SUMMARY OF CHANGES

Protocol Amendment #6

LCCC 1908: Image-Adapted Target Volumes Using 68Ga-HBED-CC PSMA-PET/MRI for Unfavorable-Risk Prostate Cancer Patients Receiving Radiation

AMENDMENT INCORPORATES:

- _X_ Editorial, administrative changes
- ____ Scientific changes
- Therapy changes
- ___ Eligibility Changes

Rationale for amendment: The purpose of this amendment is to update the protocol to support early closure of study due to low patient accrual and subsequent lack of funding. It is also important to note that 68Ga-HBED-CC PSMA-PET/MRI is no longer investigational.

Editorial, administrative changes:

Section 6.6	Language added to reflect circumstances of patient removal from the study
Section 10.3	Language added to reflect circumstances of early termination of the study

THE ATTACHED VERSION DATED July 24, 2024 INCORPORATES THE ABOVE REVISIONS

SUMMARY OF CHANGES

Protocol Amendment #5

LCCC 1908: Image-Adapted Target Volumes Using 68Ga-HBED-CC PSMA-PET/MRI for Unfavorable-Risk Prostate Cancer Patients Receiving Radiation

AMENDMENT INCORPORATES:

- X_ Editorial, administrative changes
- _X_ Scientific changes
- ____ Therapy changes
- _ Eligibility Changes

Rationale for amendment: The purpose of this amendment is to update the protocol with respect to the ⁶⁸Ga-PSMA-11 radiotracer that was once investigational and is now a commercial product. Accordingly, the language within the protocol was amended. The appendix was also updated with the most recent version of the PCSI questionnaire.

Editorial, administrative changes:

	Mechanical edits made throughout
Section 6.2	Language added referencing package insert
Section	List of required documents updated
11.2	

Scientific changes:

Section 6.1.1.1	The ⁶⁸ Ga-PSMA-11 radiotracer will now be via a commercial
	kit. Language regarding the synthesis and quality control of
	[68Ga]-PSMA removed.
Section 6.2	Investigational PSMA tracer language removed
Appendix A.5	Updated PCSI: QoL questionnaire added.

THE ATTACHED VERSION DATED April 14, 2023 INCORPORATES THE ABOVE REVISIONS

LCCC 1908: Image-Adapted Target Volumes Using 68Ga-HBED-CC PSMA-PET/MRI for Unfavorable-Risk Prostate Cancer Patients Receiving Radiation

Principal Investigator

[name] Clinical Assistant [name] of Radiation Oncology [name] [contact] (phone) [contact] (fax) Email: [contact]

Biostatistician

1.0 STUDY SCHEMA

The purpose of this study is to determine the feasibility and toxicity of using prostate-specific membrane antigen-positron emission tomography (PSMA-PET) and multi-parametric magnetic resonance imagining (mpMRI) to guide target volumes for patients with unfavorable-risk prostate cancer receiving radiation. The study schema is shown in **Figure 1**.

Figure 1. Study Schema

2.0 BACKGROUND AND RATIONALE

2.1 Study Overview

Title of the study	Image-Adapted Target Volumes Using ⁶⁸ Ga- HBED-CC PSMA-PET/MRI for Unfavorable-Risk Prostate Cancer Patients Receiving Radiation
Short description of the study	PSMA-PET/MRI Unfavorable-Risk Target Volume Pilot Study
Indication	Primary radiation therapy for localized prostate cancer
Primary objective of the study	To determine the safety of using PSMA-PET/MRI to define radiotherapy targets, while meeting all the current planning criteria.
Secondary objectives of the study	To further describe the adverse events associated with using PSMA-PET/MRI to define radiotherapy target volumes in subjects with unfavorable-risk prostate cancer. To evaluate biochemical control after radiotherapy in subjects who have received PSMA-PET/MRI to define radiotherapy target volumes.

	July 24, 2024
	To measure patient-reported quality of life prior to radiation therapy and over time in subjects with prostate cancer who have received PSMA-PET/MRI to define radiotherapy target volumes.
	To determine the proportion of screened subjects who are enrolled on the study.
Exploratory objectives of the study	
Study design	One study arm, Phase II
	Written informed consent obtained to participate in the study and HIPAA authorization for release of personal health information.
	Male subjects \geq 18 years of age
	Histologically confirmed prostate adenocarcinoma
Inclusion criteria	Unfavorable intermediate or high-risk, based on the NCCN criteria ³¹ (Appendix A.1), with appropriate staging (e.g. bone scan)
	Subject has adequate performance status as defined by ECOG performance status of 0-2. (Appendix A.2)
	Subject is willing and able to comply with the protocol as determined by the Treating Investigator.
	Subject speaks English (quality of life instrument is validated in English)
Exclusion criteria	Contraindications for MRI

	July 24, 2024
	Other prior or concomitant malignancies with the exception of:
	 Non-melanoma skin cancer Other cancer for which the subject has been disease free for ≥5 years before the first study treatment and of low potential risk for recurrence.
	Inflammatory bowel disease
Number of patients	42
Primary endpoints	The planning criteria that will be used are the current standard of care and standard practice at UNC and includes defined treatment volumes with a prescribed dose while respecting the dose constraints to all organs at risk. The primary endpoint is grade 3+ late genitourinary toxicity and gastrointestinal toxicity as classified and graded according to the National Cancer Institute's Common Terminology Criteria for Adverse Events (CTCAE), version 5.0 at 12 months after radiation therapy.
	Grade 3+ acute and late genitourinary and gastrointestinal toxicity will be defined according to CTCAE, version 5.0 during radiation therapy and at 1, 3, 6, 9, 12, 18, 24, 30, 36, 42, 48, 54 and 60 months post radiotherapy.
Secondary endpoints	Biochemical control will be defined according to the Phoenix criteria33 (PSA rise of 2 ng/mL over nadir) at 2 and 5 years after radiation therapy.
	Patient reported quality of life will be measured using the Expanded Prostate Cancer Index Composite (EPIC-26) and the Urinary Obstruction/Irritation scale of the validated Prostate Cancer Symptom Indices (PCSI). Patient reported quality of life will be measured before the start of radiation therapy at 1, 3, 6, 9, 12, 18, 24, 30, 36, 42, 48, 54, and 60 months post radiotherapy.
	The total number of subjects enrolled on the study will be compared to the total number of screened subjects.

	July 24, 2024
	The feasibility of meeting dose constraints will be defined as the proportion of subjects who meet the following dose constraint criteria:
	• SBRT-CK boost dose prescription: 6.5Gy
	• SBR1-CK boost dose prescription: 6.3Gy x 3 • PTV: V19.5Gy > 95% • PTVmax > 150%, CI < 1.8 • CTV: V19.5Gy > 99% • DIL: V24.0Gy > 99% • SBRT-CK boost dose constraints: • Rectum • V21.1Gy < 5 % • V18.9Gy < 20 % • V17.5Gy < 10 % • V16.2Gy < 40 % • V10.2Gy < 60 % • V19.5Gy < 1cc • Max < 21.2Gy • Bladder • V21.1Gy < 5 % • V19.5y < 5 cc • V9.3Gy < 40 % • Max < 21.2Gy • Prostatic Urethra • V19.5Gy > 95% • V22Gy < 0.03cc • Membranous Urethra • V18 Gy < 50% • Large bowel • V15Gy < 1cc • Small bowel • V15Gy < 1cc • Penile bulb • V15Gy < 3cc Performance of PSMA-PET/MRI to PSMA PET/CT as defined as:
3	• Rate of identification and delineation of
	• Rate of identification and defineation of DIL
	 Compared to a gold standard of image-guided prostate biopsy Rate of identification of positive pelvic
	nodes

	Rate of identification of distant metastatic disease in the pelvis
	Rate of identification of positive pelvic nodes by PSMA-PET and therefore the proportion of patients who have pelvic nodes included in the radiation field.
Schedule	 Start: January 2023 Recruitment period: 24 months Provisional conclusion: January 2026 for primary endpoint
	Study will terminate with the completion of the last follow-up in the last enrolled patient, unless study ends
Participating centers	Single center

2.2 Study Synopsis

The goals of this pilot trial are to:

- 1. Test the safety and feasibility of designing the radiation treatment plan so that the entire prostate receives the prescribed dose of radiation in addition to the visible tumor in the prostate (as detected by mpMRI and/or PSMA-PET (i.e. dominant intra-prostatic lesion (DIL))) receiving any inevitable intrinsic plan "hot spots" or areas of dose above the prescription
- 2. Test the safety and feasibility of designing the radiation treatment plan so that the pelvic lymph nodes are covered (or not covered) depending on whether visible tumor is detected by mpMRI and/or PSMA-PET imaging.

It should be noted that the prescription dose given in this study will be no different than current practice and that all radiation plans have hot spots. This study will focus the hot spots on regions determined by mpMRI + PSMA-PET to have visible tumor as opposed to the current practice where hot spot regions are randomly located in the target. Additionally, it should be noted that it is not a consensus as to whether pelvic nodes should be treated in addition to the prostate in this unfavorable risk population and that practice patterns as to whether the pelvic notes are treated differ. Simply, this study aims to determine if mpMRI and PSMA-PET imaging can help optimize 1) the location of the high dose region of SBRT-CK and 2) pelvic lymph node coverage. As all radiation plans designed and delivered to the patient as part of this trial will follow current standards on respecting dose constraints to organs surrounding the prostate and pelvic lymph nodes, including urethra, bladder, small bowel, and rectum, we do not expect the toxicities to differ from those observed in standard of care practices.

Of note, the imaging agent, PSMA, has usage guideline-dictated by other countries and we do not anticipate any toxicity or safety issues as they relate to the PSMA itself. To our knowledge, there have been no reported substantive adverse effects due to its use. 1,2

The feasibility questions: Is it possible to design "smarter" radiation plans for enrolled patients that covers the entire prostate (standard), respects all dose constraints to surrounding organs (standard), and also preferentially place the inevitable hot spots at the image-identified lesion within the prostate, all without violating the standard dose constraints for the normal tissues (organs at risk)? Furthermore, is it possible to more intelligently make the decision of whether or not to treat the pelvic lymph nodes with guidance from imaging results?

The safety question: Does delivering this treatment to the patient lead to increased side effects (compared to historical data)?

2.3 Investigational Imaging Background

Interest in using ⁶⁸Ga-PSMA PET/CT in the setting of unfavorable risk and biochemically recurrent prostate cancer has increased tremendously since it was introduced in 2012.³ Regarding radiation field design, PSMA-PET has been shown to influence the radiation planning in nearly 50% of patients with high risk disease (includes patients with recurrent disease as well as those at initial presentation).^{4,5} In a prospective study of 108 unfavorable risk prostate cancer patients at initial presentation, PSMA-PET imaging influenced treatment design in 21% of patients.⁶ Further, Dewes et al. conducted a retrospective study of 15 patients and evaluated the utility of PSMA-imaging and if it influenced the radiation treatment target volumes. They found the radiation concept changed in 33% of all patients, leading to relevant changes in the planning target volumes, including an additional irradiation of the pelvic lymph nodes due to tracer uptake in 25% of patients.⁷ Therefore it is likely PSMA-PET/CT can be useful in radiation field design.

Corfield et al. conducted a systematic review of ⁶⁸Ga-PSMA PET for primary staging of high-risk prostate cancer and concluded, based on 12 studies of 322 patients, it outperforms traditional imaging modalities.⁸ Their study included the results from Budaus et al. who conducted a retrospective study of 608 lymph nodes removed from men with high risk prostate cancer who had preoperative ⁶⁸Ga-PSMA-PET/CT scans and compared them to histologic findings after radical prostatectomy with lymph node dissection. They found the sensitivity, specificity, positive predictive value, and negative predictive value of ⁶⁸Ga-PSMA-PET/CT for lymph node metastasis detection were 33.3%, 100%, 100%, and 69.2%, respectively.⁹ In a recent systematic review and meta-analysis, the following predictive ability of PSMA-PET imaging for primary staging purposes was found. Incorporating the results of five different studies with a total of 244 high and intermediate risk prostate cancer patients, on a per-lesion analysis the summary sensitivity and specificity were 75% and 99%, respectively. On a per-patient analysis the summary sensitivity and specificity were 77% and 97%, respectively.¹⁰

CONFIDENTIAL UNIVERSITY OF NORTH CAROLINA July 24, 2024

Regarding nodal radiation, there are three published large randomized controlled trials looking at the role of pelvic nodal irradiation in nonmetastatic prostate cancer which have proved inconclusive.^{11–13} More recently, a randomized study conducted at a single institution in India (POP-RT, Murthy et al., JCO 2021) demonstrated improvements in biochemical failure free survival, disease free survival, and distant metastasis free survival with the addition of pelvic radiotherapy in patients with a nomogram-predicted risk of occult nodal metastasis exceeding 20%.¹⁴ There are two more trials currently underway (NCT01368588; PEACE 2 - GETUG - AFU 23) with estimated primary completion dates in 2025-2027.^{15,16} Collectively, these studies demonstrate the clinical equipoise in this area (whether or not to include nodes in the treatment field), which has been an area of intense debate for at least two decades (Nguyen & D'Amico, JCO 2008; Roach, JCO 2008).^{17,18}

Regarding defining intraprostatic lesions, ⁶⁸Ga-PSMA-PET alone has not been perfect. One meta-analysis found in seven studies that PSMA-expressing lesions were identified in only 203 of 273 patients (74%).¹⁹ However, this number appears to be confounded by lymph node detection rates. When looking at PSMA-PET defined DILs alone, the detection rates could be over 95%,²⁰ and may be even higher in high-risk disease which have greater PSMA-PET avidity.²¹ Three separate studies have shown that MRI and PSMA can deliver complimentary information on the localization of DILs.^{22–24} Therefore, it is likely PSMA PET-MRI is advantageous to PSMA PET-CT alone in identifying DILs. In a slice-by-slice analysis with histopathology, the sensitivity for PSMA PET alone, mpMRI alone, and PSMA PET-MRI combined, was 75%, 70%, and 82%, respectively for prostate cancer tumor detection. The specificity was 87%, 82%, and 67%, respectively.²⁵ Others have also found PSMA-PET/MRI to be superior to multiparametric MRI alone in detecting prostate cancer.²⁶

The concept of biological-guided (e.g. with PET) dose escalation (e.g. to DILs) is not new,²⁷ but has never been done with in combination with SBRT-CK. A feasibility study such as the current study under investigation will be the first step to investigating this question. Based on other studies, know that dose escalation in prostate cancer improves progression free survival.^{28,29}

Other nations have been quicker to explore ⁶⁸Ga-PSMA-PET/CT imaging for prostate cancer and guideline standards have been developed in Europe in regards to the recommendation, performance, interpretation and reporting of PSMA-PET/CT for prostate cancer imaging. One such endorsed use is for primary staging in high-risk disease before planning external beam radiation.¹ Additionally, the Australian and New Zealand Radiation Oncology Genito-Urinary group recommends considering PSMA-PET in the setting of recurrent disease post-prostatectomy at low PSA levels because of its sensitivity over other imaging modalities.²

Importantly, for all of these studies, the impact on patient-reported quality of life of this approach has not been described.

Furthermore, in published literature, probability of tumor control for prostate cancer has been associated with radiation dose. Martinez et al.³⁰ showed that a dose of EQD₂ > 100 Gy (using $\alpha / \beta = 1.2$ Gy) had a significant effect on the recurrence rate of prostate cancer. Converting this EQD2 dose to clinical practice, as relevant for the current pilot trial, we will increase area of visible tumor to receive at least EQD2 > 100 Gy.³⁰

2.4 Rationale

Radiation therapy is a standard curative option for patients with localized prostate cancer. At UNC, patients with unfavorable intermediate and high-risk prostate cancer are offered radiation usually given with a long course (18 months) of androgen deprivation therapy. The radiation can be given as moderately hypoefractionated radiotherapy alone, or with with a combination of conventionally fractionated external beam radiation therapy (EBRT) (25 daily treatments) and boost utilizing stereotactic body radiotherapy (SBRT) with CyberKnife (CK). Our standard practice is to include the pelvic nodes in our treatment field, although as previously discussed this topic is controversial. These are standard treatment options according to NCCN guidelines.³¹ With current standard radiation doses, 5-year recurrence-free survival is reported to be 83% (unfavorable risk disease). Additionally, when the radiation fields are designed, the primary tumor location within the prostate is not typically taken into account, rather, the entire prostate is treated uniformly.

The availability of the PET-MRI facility at UNC (Biomedical Research Imaging Center, BRIC) uniquely allows us to examine these clinically-relevant questions using an mpMRI/PSMA-PET scan. Patients participating on this trial will have, using the same injection, an mpMRI/PSMA-PET scan and a PSMA-PET/CT scan, both of which will be used to help with radiation design. The long-term goal of this line of research is to allow smarter radiation design in the future that more specifically targets the tumor(s), therefore maximizing the therapeutic window (by focusing treatment more where there is cancer and not treating where there is no cancer). There is significant long-term potential for this research as imaging continues to improve and PSMA-PET/mpMRI becomes more widely adapted. UNC's PET-MRI is one of only a few in the country, which positions UNC to be a leader in the development of this technology. This study will also help create new knowledge in terms of comparability of PET/MR and PET/CT, and how the information gained on PET/MR could potentially be transferred to PET/CT, the latter of which is more widely available.

Image-adapted prostate irradiation

Currently, all radiation treatment is designed to treat the entire prostate to a prescribed dose. However, improvements in imaging, such as with multiparametric MRI (mpMRI) and PSMA-PET, which can be used to visualize tumor locations within the prostate, allow exploration of smarter radiation designs that concentrate the inevitable heterogeneous hot spots in a radiation plan on the area(s)

CONFIDENTIAL UNIVERSITY OF NORTH CAROLINA July 24, 2024

of visible tumor. Specifically, mpMRI has already revolutionized the way prostate biopsies are performed to diagnose or follow men with prostate cancers. Historically, prior to the availability of mpMRI when prostate tumors cannot be visualized, biopsies are done with random sampling of the prostate. More recently, clinical trials have shown that mpMRI-guided prostate biopsies are better than random sampling biopsies in diagnosing high-grade, clinically relevant prostate cancer.³² This same targeted approach of diagnosis can be adapted to radiation treatment.

Image-adapted pelvic nodal irradiation

Currently, patterns of practice vary as to whether the pelvic lymph nodes are included in the radiation field for men with unfavorable risk prostate cancer. The NCCN simply states "prophylactic nodal radiation can be considered".³¹ Improvements in imaging may allow the exploration of smarter radiation design by better identifying the subset of men who would stand to benefit from the inclusion of pelvic lymph nodes in the radiation field. Specifically, mpMRI and PSMA-PET may better identify lymph node involvement, and thus their inclusion in the radiation fields.

3.0 STUDY OBJECTIVES

3.1 **Primary Objective**

3.1.1 To determine the safety of using PSMA-PET/MRI to define radiotherapy targets, while meeting all the current planning criteria.

Hypothesis: Using PSMA-PET/MRI to define radiotherapy targets in patients with unfavorable-risk prostate cancer does not increase toxicity at 1 year after radiation, relative to historical controls.

3.2 Secondary Objectives

- **3.2.1** To further describe the adverse events associated with using PSMA-PET/MRI to define radiotherapy target volumes in subjects with unfavorable-risk prostate cancer.
- **3.2.2** To evaluate biochemical control after radiotherapy in subjects who have received PSMA-PET/MRI to define radiotherapy target volumes.
- 3.2.3 To measure patient-reported quality of life prior to radiation therapy and over time in subjects with prostate cancer who have received PSMA-PET/MRI to define radiotherapy target volumes.
- **3.2.4** To determine the proportion of screened subjects who are enrolled on the study.

3.3 Exploratory Objectives

4.0 STUDY ENDPOINTS

4.1 Primary

The planning criteria that will be used are the current standard of care and standard practice at UNC and includes defined treatment volumes with a prescribed dose while respecting the dose constraints to all organs at risk. The primary endpoint is grade 3+ late genitourinary toxicity and gastrointestinal toxicity as classified and graded according to the National Cancer Institute's Common Terminology Criteria for Adverse Events (CTCAE), version 5.0 at 12 months after radiation therapy.

- 4.2 Secondary
- 4.2.1 Grade 3+ acute and late genitourinary and gastrointestinal toxicity will be defined according to CTCAE, version 5.0 during radiation therapy and at 1, 3, 6, 9, 12, 18, 24, 30, 36, 42, 48, 54 and 60 months post radiotherapy. Additionally, this will be reported as a cumulative incidence over the entire 5-year course of the study.
- 4.2.2 Biochemical control will be defined according to the Phoenix criteria³³ (PSA rise of 2 ng/mL over nadir) at 2 and 5 years after radiation therapy.
- 4.2.3 Patient reported quality of life will be measured using the Expanded Prostate Cancer Index Composite (EPIC-26) and the Urinary Obstruction/Irritation scale of the validated Prostate Cancer Symptom Indices (PCSI). Patient reported quality of life will be measured before the start of radiation therapy at 1, 3, 6, 9, 12, 18, 24, 30, 36, 42, 48, 54, and 60 months post radiotherapy.
- 4.2.4 The total number of subjects enrolled on the study will be compared to the total number of screened subjects.
- 4.2.5 The feasibility of meeting dose constraints will be defined as the proportion of subjects who meet the following dose constraint criteria:
 - SBRT-CK boost dose prescription: 6.5Gy x 3
 - PTV: V19.5Gy > 95%
 - PTVmax > 150%, CI < 1.8
 - CTV: V19.5Gy > 99%
 - \circ DIL: V24.0Gy > 99%

- SBRT-CK boost dose constraints:
 - o Rectum
 - V21.1Gy< 5 %
 - V18.9Gy< 20 %
 - V17.5Gy<10 %
 - V16.2Gy< 40 %
 - V10.2Gy< 60 %
 - V9.3Gy< 40 %
 - V19.5Gy<1cc
 - Max<21.2Gy
 - Bladder
 - V21.1Gy< 5 %
 - V19.5y < 5 cc
 - V9.3Gy<40 %
 - Max<21.2Gy
 - Prostatic Urethra
 - V19.5Gy > 95%
 - V22Gy < 0.03cc
 - Membranous Urethra
 - V18 Gy < 50%
 - Large bowel
 - V15Gy<1cc
 - Small bowel
 - V15Gy<1cc
 - Penile bulb
 - V15Gy< 3cc

4.2.6 Performance of PSMA-PET/MRI to PSMA PET/CT as defined as:

- Rate of identification and delineation of DIL (e.g. sensitivity and specificity)
 - Compared to a gold standard of image-guided prostate biopsy
- Rate of identification of positive pelvic nodes
- Rate of identification of distant metastatic disease in the pelvis
- 4.2.7 Rate of identification of positive pelvic nodes by PSMA-PET and therefore the proportion of patients who have pelvic nodes included in the radiation field.

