7.1.4 Adverse Events

Events should be assessed per NCI-CTCAE criteria 5.0. Information regarding occurrence of adverse events will be captured throughout the study. Duration (start and stop dates), severity/grade, outcome, treatment and relation to study treatment will be recorded in the case report form. A dose-limiting toxicity is defined as all Grade 3 or above acute toxicities attributed to the treatment under study. The accrual will be halted if the number of patients with dose-limiting toxicities equals to or exceeds a rate of 30%.

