10.0 STATISTICAL CONSIDERATIONS

10.1 Study Design/Study Endpoints

This will be a prospective, single-arm, non-randomized, phase II study to examine the feasibility and acute and late toxicities of standard radiation treatment for unfavorable intermediate and high risk prostate cancer - this involves a combination of external beam radiation therapy and SBRT-CK and androgen deprivation therapy – while using advanced imaging modalities (PSMA/PET-mpMRI) to intelligently adapt the radiation fields. The radiation therapy usually takes 2 months and the follow up is 60 months, while the duration of the evaluation of the final results will be about 12 months after the end of treatment.

There is one primary endpoint:

(1) Late genitourinary toxicity and gastrointestinal toxicity at 12 months (these will be recorded at 1, 3, 6, 9, 12, 24, 36, 48 and 60 months after radiotherapy, according to CTCAE v5).

Table 1 shows an overview of late toxicities in randomized studies of conventionally fractionated schemes in primary prostate carcinoma. On average, the rate of late GI / GU toxicities of grade 2 or higher averaged a rate of approximately 16%.

Study	1 ³⁸	2 ³⁹	3 ⁴⁰	4^{41}	5 ⁴²	6 ⁴³				
Patient #	296	151	101	478	372	1065				
Total dose (Gy)	76	76	75.6	86.4	76	74				
Fractions #	38	38	42	39	38	37				
Dose/fraction (Gy)	2	2	1.8	2	2	2				
Late Reactions – RTOG G2+										
GI (%)	9	22.5	5.1	3.7	8	13.7				
GU (%)	19	13.4	16.5	15.5	24	9.2				

 Table 1 Summary of results from recent clinical trials with external beam radiotherapy.

Table 2 shows an overview of late toxicities in randomized studies of combination external beam radiotherapy and SBRT in primary prostate carcinoma. On average, the rate of late Grade 2 or higher GU toxicities is $\sim 11.4\%$ and for GI toxicities $\sim 6\%$.

Table 2 Summary of results from randomized	clinical	trials	treating	with	combination
external beam radiation therapy and SBRT.					

Study	1 ⁴⁴	2 ⁴⁵	3 ⁴⁶	4 ⁴⁷	5 ⁴⁸	6 ⁴⁹	7 ⁵⁰	8 ⁵¹
Patient #	121	26	76	39	108	48	41	45
EBRT dose (Gy)	45	44	46	45	45-50.4	45	45	45
EBRT Fractions #	25	20	23	25	25-28	25	25	25
CK dose (Gy)	21	18 or 21	18	21	19.5	19 or 21	21	18-21
CK Fractions #	3	3	3	3	3	2	3	3
		Late T	'oxicity –	Grade 2	+			
GI (%)	3.4	4.0	9.3	12.8	5.0	0.0	0.0	13.3
GU (%)	20.6	4.0	1.4	10.3	13.7	27.0	11.0	2.9

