We denote p the probability that a patient experiences a late grade 2+ GU/GI toxicity. We want p to be small enough to claim the new imaging strategy (PSMA/PET-mpMRI) as feasible with no greater late toxicity. Specifically, the null and alternative hypotheses are:

$H_0: p \ge 0.30 \ vs \ H_1: p \le 0.15$

That is, we accept the claim that the new strategy is safe if the observed toxicity rate is not too high, and hope to reject the claim (H0) with sufficient power when the true toxicity rate is about 20%. With a sample size of 38, we reach 80% power to reject (if we observe ≤ 7 cases with late toxicity) the null hypothesis (H0) at alpha = 0.1. To account for 10% loss follow-up, we will enroll 42 patients to ensure 38 evaluable patients.

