10.3 Data Analysis Plans

Analysis of primary endpoint, late toxicity rates, to decide whether to reject the null hypothesis, will be conducted as described above. In addition, the estimated acute and late toxicity rates will be reported with 95% confidence intervals in the final analysis.

As per the analyses of secondary outcomes, binary outcomes like (1) 2 and 5 years biochemical control according to the Phoenix criteria; (2) local recurrence rate after 2 and 5 years (defined by biopsy); and (3) rate of screened to truly included patients and compliance with dose restrictions, will be summarized by estimated proportions and associated 95% confidence intervals. Numerical outcomes like (4) quality of life (according to EPIC-26 and PCSI) will be summarized using descriptive (mean and standard deviation, median and range) statistics. Exploratory

correlation analyses will be conducted to identify biomarkers correlated with the diagnosis and the course of the disease, as well as gastrointestinal and urogenital toxicity.

In the event of an early termination of this study, the same analysis plan as described above will be followed, but based on the data available at the time of study termination.

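### The declared primary endpoint is grade 3+ late GU/GI toxicity, but the only hypothesis test is built on grade 2+

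*Combined protocol and SAP*

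**What the plan says.** Sections 2.1 (synopsis) and 4.1 use the same sentence: "The primary endpoint is grade 3+ late genitourinary toxicity and gastrointestinal toxicity", graded by CTCAE v5.0 at 12 months after radiation.

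Section 10.1 lists the single primary endpoint as "Late genitourinary toxicity and gastrointestinal toxicity at 12 months", with no grade. It then summarises historical late toxicity, all of it grade 2 or higher. For external beam alone (Table 1) it says "On average, the rate of late GI / GU toxicities of grade 2 or higher averaged a rate of approximately 16" per cent; for external beam plus SBRT (Table 2 of 10.1) it gives about 11.4% GU and 6% GI. The test follows: "We denote p the probability that a patient experiences a late grade 2+ GU/GI toxicity", with H0: p ≥ 0.30, H1: p ≤ 0.15, 38 evaluable patients, alpha 0.1, 80% power, and rejection of H0 at 7 or fewer cases. The same paragraph also speaks of power "when the true toxicity rate is about 20" per cent.

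Section 10.3 adds no definition: "Analysis of primary endpoint, late toxicity rates, to decide whether to reject the null hypothesis, will be conducted as described above". On early termination it keeps the same plan, "based on the data available at the time of study termination".

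Section 4.2.1 already lists grade 3+ acute and late GU/GI toxicity, including at 12 months, as a secondary endpoint.

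**The concern.** The event that defines success in the endpoint sections is not the event that is tested. A report that follows 4.1 has no pre-specified test. A report that follows 10.1 tests something other than the declared primary endpoint.

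The choice can reverse the conclusion. Suppose 9 of 38 patients have a late grade 2+ event and 2 of those are grade 3+. Under 10.1, 9 > 7 and the strategy is not shown to be safe. If the same rule is applied to the 4.1 event, 2 ≤ 7 and it is declared safe. An author who sees the data before the grade is settled could choose between these.

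The stopping boundaries in 10.2 do not settle it. They govern accrual and cover grade 4 toxicity and grade 3+ DLTs, and sections 6.4 and 7.1.4 define DLTs as acute.

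**Working it through.** **Inputs (10.1).** n = 38; reject H0 if X ≤ 7; p0 = 0.30; p1 = 0.15; alpha = 0.10, one-sided by the form of the hypotheses. The second rate named for power is about 20%.

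**Formula.** Exact binomial: P(X ≤ 7) = Σ C(38, k) p^k (1 − p)^(38 − k), summed over k = 0 to 7.

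**Step 1: reproduce the plan's figure on grade 2+.**
- p = 0.30: 0.0795, within 0.10. A cut-off of 8 would give 0.1518, so 7 is the largest valid cut-off.
- p = 0.15: 0.7986. The stated 80% power reproduces.
- p = 0.20: 0.5003. The 80% does not hold at the other rate named in the paragraph.

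The design is therefore sound arithmetic for grade 2+ at 15%.

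**Step 2: put grade 3+ counts into the same rule.** The documents give no late grade 3+ rate, so these true rates are assumptions.

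| Assumed true grade 3+ rate | P(safe declared) |
|---|---|
| 5% | 0.9995 |
| 8% | 0.9907 |
| 10% | 0.9682 |
| 12% | 0.9218 |
| 15% | 0.7986 |
| 20% | 0.5003 |
| 25% | 0.2313 |

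Up to about 10–12%, the rule would hardly ever flag a problem.

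**Step 3: can a 30% null be read as a grade 3+ benchmark?** Grade 3+ cannot exceed grade 2+, so bound the share of patients with either a GI or a GU grade 2+ event in each study. The lower bound is the larger of the two rates (full overlap); the upper bound is their sum (none). This assumes that GI and GU share a denominator within a study.
- Table 1, lower: (19 + 22.5 + 16.5 + 15.5 + 24 + 13.7)/6 = 111.2/6 = 18.5%. Upper: (28 + 35.9 + 21.6 + 19.2 + 32 + 22.9)/6 = 159.6/6 = 26.6%.
- Table 2 of 10.1, lower: 111.7/8 = 14.0%. Upper: 138.7/8 = 17.3%.

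On unweighted averages, 30% lies above even the no-overlap bound for grade 2+. The tables give no support for it as a grade 3+ null.

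**Step 4: what a grade 3+ test at n = 38 would look like.** Assumed nulls, exact alpha ≤ 0.10:

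| Assumed p0 | Cut-off | Power at 2% | Power at 5% |
|---|---|---|---|
| 15% | ≤ 2 | 0.96 | 0.70 |
| 10% | ≤ 1 | 0.82 | 0.43 |
| 8% | 0 | 0.46 | 0.14 |
| 5% | none: P(0 events) = 0.142 | – | – |

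Changing the grade alone therefore cannot preserve the present cut-off and power claim.

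**Step 5: early closure.** If fewer than 38 patients are evaluable, P(X ≤ 7 at p = 0.30) is 0.281 at n = 30, 0.512 at n = 25 and 0.772 at n = 20. These sizes are illustrative; the documents do not give the final number.

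**The case against.** The strongest reply is that the test itself is clear. Section 10.3 points back to 10.1, where p is explicitly grade 2+ with its own hypotheses, sample size and cut-off, and no sentence applies that rule to grade 3+. A grade 3+ primary endpoint would also largely duplicate 4.2.1, which suggests a drafting slip in 2.1 and 4.1. On this view, Step 2 and the opposite-verdict example describe something the protocol never prescribes.

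Much of this is fair, and Step 2 is conditional. But inferring a slip is not specifying an endpoint. Even on this reading, the declared primary endpoint is left without a test.

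Step 3 has limits too. It concerns averages: within Table 1, the no-overlap sums reach 35.9% in study 2 and 32% in study 5. Table 1 is graded by RTOG, not CTCAE v5.0. These points weaken the comparison but supply no late grade 3+ benchmark.

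Finally, the study is closing for low accrual, so a verdict on 38 patients may never be reached. Grade 4 and acute grade 3+ monitoring, grade 3+ reporting under 4.2.1 and 95% confidence intervals limit the consequence for safety. That stands. It does not make the point moot, because 10.3 carries the same plan over to whatever data exist, and the primary event must still be named.

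**Conclusion.** The inconsistency is real, lies in current operative text, and needs correction before the primary analysis. The sample size, cut-off, alpha and 80% power are correct for late grade 2+ toxicity at a true rate of 15%; the fault is which event they describe. The contradiction rests on no assumption. The size of the effect under a grade 3+ reading does: it depends on assumed true rates and on someone applying the rule of 7 to grade 3+ counts. Under those conditions, safety is declared with probability 0.92 or more at any true rate up to 12%.

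**What to change.** State grade 2+ in the primary endpoint text of 2.1 and 4.1 and in the endpoint line of 10.1, with one event wording and one window in all three. One possibility is at least one CTCAE v5.0 grade 2+ GU or GI toxicity from more than 3 months through the 12-month visit. This would reconcile an assessment at 12 months with a probability of experiencing an event, and it fits the definition of late in 6.2; the choice of window is the sponsor's. Keep grade 3+ as the secondary endpoint in 4.2.1. Sample size, cut-off, alpha and power at 15% are unchanged.

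If grade 3+ is intended, replace H0, H1, the cut-off and the power statement with values justified from late grade 3+ data, and revisit the sample size.

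Two related corrections belong in the same amendment. Make the power sentence agree with the 15% alternative, or report 50% power at 20%. State in 10.3 that with fewer than 38 evaluable patients the count of 7 is not carried over on either grade, and that the rate is reported with its 95% confidence interval.

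The cost is a short dated amendment: three places for the grade, plus the early-termination sentence in 10.3. No new data are needed, since section 7.1.4 already provides that "Duration (start and stop dates), severity/grade, outcome, treatment and relation to study treatment will be recorded in the case report form". The downsides are a higher reported primary event rate than under grade 3+, and a late clarification that must be disclosed as post hoc if outcome data have been seen.
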